6.1 Anticipated Toxicities

A list of the adverse events and potential risks associated with the agents administered in this study appear below and will determine whether dose delays and modifications will be made or whether the event requires expedited reporting **in addition** to routine reporting.

6.1.1 Adverse Event List for IL-2

IL-2 (Proleukin) is a commercial agent. The relevant side effects of low-dose IL-2 in HSCT patients are described below. Additional detailed toxicity information may be found in the Proleukin package insert that relates primarily to high-dose IL-2.

- Local Reaction

CONFIDENTIAL

This document is confidential. Do not disclose or use except as authorized.

Phase II ECP and IL-2 for chronic GVHD

Version 2.0; August 15, 2016

Most patients receiving daily SC low-dose IL-2 reported injection site reactions, typically focal erythema that resolved in a few days; and induration that resolved after 2-3 weeks. Dose interruptions were occasionally required in patients with more marked induration (CTC grade 3). Lengthy dose interruptions may result in patients being unevaluable for response (Section 6.2)

- Constitutional symptoms

In the HSCT setting, some patients on low-dose IL-2 developed fever, nausea and arthralgia within 72 hours of starting IL-2. Interruption of therapy resulted in symptom resolution with 3 days. Patients tolerated re-introduction of IL-2 at lower dose, with subsequent escalation to MTD dose.

- Thyroid dysfunction

Thyroid function test abnormalities were noted in some HSCT patients on low-dose IL-2. Only one patient however developed clinical hypothyroidism necessitating therapy while on IL-2. After cessation of IL-2, thyroid function returned to normal. Hence, a thyroid panel (TSH, T4, free T4) levels will be checked at study entry and week 12 while on study. Patients with evidence for hypothyroidism will be worked up (antimicrosomal, antithyroglobulin antibodies) and given replacement thyroxine as clinically indicated.

- Hematopoiesis

Early post-HSCT, low-dose IL-2 caused an initial decrease in the absolute lymphocyte count in most patients after 1 week of therapy. Thereafter, with continued infusion, a steady increase in lymphocyte count occurred in all patients. Low dose IL-2 also caused an initial increase in eosinophil counts (peak at 3 weeks) followed by a gradual decline. No changes in monocyte or neutrophil counts were observed.

The platelet count decreased by >20% in some HSCT patients on low-dose IL-2. This decrease was noted within the first 2 weeks on IL-2, and continued treatment was not associated with further declines in platelet count. No patients had >40% decline in platelet counts, and none required platelet transfusions or had bleeding episodes.

6.1.2 Adverse Event Lists for Other Agents

There is toxicity related to cGVHD and to the immune suppressive medications used in its treatment. These toxicities are routinely managed by the study investigators. For a comprehensive list of adverse effects, please refer to the package inserts of the individual immune suppressive agents

6.2 Dose Modifications/Delays

Toxicities are to be assessed according to the NCI Common Toxicity Criteria for Adverse Events (CTCAE), Version 4.0 (Appendix H; section 17.8)

- Anaphylaxis: Life threatening anaphylaxis related to IL-2 requires discontinuation of IL-2.
- Thrombotic microangiopathy: TMA during IL-2 therapy requires discontinuation of IL-2 if it is associated with CNS dysfunction, renal dysfunction requiring hemodialysis/CVVH, or need for hospitalization.
- CTC Grade 4 toxicity: Grade 4 non-hematologic toxicity related to IL-2 requires discontinuation of IL-2, unless it is an asymptomatic correctable lab test abnormality (e.g. uric acid).
- CTC Grade 3 toxicity: IL-2 will be withheld for Grade 3 non-hematologic toxicities related to IL-2, unless it is an asymptomatic and correctable lab test result abnormality (e.g. uric acid). If the toxicity resolves to grade 1 or below within 2 weeks, IL-2 can be restarted at 50% dose that will not be re-escalated. If the toxicity does not resolve in 2 weeks to grade 1 or below, or recurs to grade 3 or above after restarting IL-2, it will be discontinued. IL-2 may also be withheld for Grade 3 non-hematologic toxicities unrelated to IL-2 per physician discretion. If withheld, subsequent management is suggested per above guidelines.
- Expected non-hematologic toxicity: IL-2 can be withheld and/or restarted at 50% dose for less than grade 3 toxicity (local site reactions, persistent constitutional symptoms) depending on patient tolerability and the discretion of the treating physician.

CONFIDENTIAL

This document is confidential. Do not disclose or use except as authorized.

Phase II ECP and IL-2 for chronic GVHD

Version 2.0; August 15, 2016

- Severe hematologic toxicity: IL-2 will be withheld for severe declines in peripheral counts (ANC<500, Plts<10,000) not related to malignant disease relapse, infection or other etiologies. If counts improve (ANC>1000, Plts>20,000) within 2 weeks, IL-2 will be restarted at 50% dose and not re-escalated. If peripheral counts do not improve within 2 weeks, or drop again (ANC<500, Plts<10,000) after restarting IL-2, it will be discontinued.
- Worsening of cGVHD: Clinical signs of worsening cGVHD while on IL-2 that require the addition of a new immunosuppressive medication (at the discretion of the treating physician), will be a criterion for IL-2 discontinuation. An increase in the corticosteroid dose above baseline will be considered evidence of worsening cGVHD. Changes in other immunosuppressive medication doses to maintain a therapeutic level alone will not be criteria for discontinuation of IL-2 or considered evidence of cGVHD worsening.
- Infection: Of note, infection during IL-2 treatment is not considered IL-2 related, since both cGVHD and the concurrent use of immune suppression medications are known risk factors for infection. Infection is therefore considered an expected complication of cGVHD. However, patients who develop a CTC grade 3 or higher infection prior to week 6 of IL-2 therapy will have IL-2 withheld. They can be considered for restarting IL-2 at their prior dose after control of infection, at the discretion of the treating physician.

CONFIDENTIAL

This document is confidential. Do not disclose or use except as authorized.

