2.2.1.4 Clinical Experience

In DFCI 07-083, we assessed safety of low-dose interleukin-2 in participants with refractory active cGVHD. ⁴¹ The primary objective was to determine the MTD and toxicity of an 8-week course of low-dose IL-2 in chronic GVHD participants with an inadequate response to steroids. Eligibility included cGVHD that had not responded to at least 0.25 mg/kg prednisone for a 4 week period, the absence of infection, and stable doses of immune suppression for 4 weeks prior. The study had a Phase 1 dose escalation design with 3 dose levels ($0.3-, 1-, 3-; \times 10^6$ IU/m²/day for 8 weeks).

29 participants accrued: 28 evaluable for toxicity; 23 for response. IL-2 at 1×10^6 IU/m²/day was determined to be MTD. Two participants developed dose-limiting-toxicity (thrombotic microangiopathy). None experienced GVHD flare. There was no malignant disease relapse. 12 of 23 participants had objective clinical responses. Low-dose IL-2 selectively increased Treg counts in-vivo (Figure 1) without impacting conventional CD4+ T (Tcon) counts. The Treg:Tcon ratio also rose (Figure 2). NK cell counts rose to a lesser extent. Low-dose IL-2 did not impact CD8+ T, B, or NKT counts. Treg count and Treg:Tcon ratio remained elevated at 8 weeks of IL-

CONFIDENTIAL

This document is confidential. Do not disclose or use except as authorized.

Phase II ECP and IL-2 for chronic GVHD

Version 2.0; August 15, 2016

2, then declined off IL-2. IL-2-induced Treg expressed FoxP3+ and were functional in Tcon suppression assays. Importantly, clinical and immunologic responses were sustained in responders on extended-duration IL-2 therapy beyond 12 weeks, enabling a taper of concomitant immunosuppression.

Figure 1 (below left). Expansion of CD4 Treg during treatment with daily low-dose IL-2. Gating on CD3+CD4+ T, Treg are defined as CD25+CD127- (black) and Tcon are CD25-CD127+ (blue). The %Treg within the CD4 gate is indicated in each plot. Figure 1 depicts a representative patient on Dose Level B.

[figure not shown]

Figure 1

[figure not shown]

Figure 2

Figure 2 (above right): Median Treg:Tcon ratio on IL-2 therapy. There was a rapid rise and sustained plateau within a few weeks of starting IL-2, and a decline after stopping IL-2. Medians with inter-quartile range are shown.

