- Renal: Serum creatinine within normal institutional limits or creatinine clearance ≥ 60 mL/min/1.73 m² for participants with creatinine levels above institutional normal.
- Pulmonary: FEV1 $\geq 50\%$ or DLCO(Hb) $\geq 40\%$ of predicted, unless pulmonary dysfunction is deemed to be due to chronic GVHD.
- Adequate bone marrow function indicated by ANC $>1000/\text{mm}^3$ and platelets $>50,000/\text{mm}^3$ without growth factors or transfusions
- Cardiac: No myocardial infarction within 6 months prior to enrollment or NYHA Class III or IV heart failure, uncontrolled angina, severe uncontrolled ventricular arrhythmias, or electrocardiographic evidence of acute ischemia or active conduction system abnormalities. Prior to study entry, any ECG abnormality at screening must be documented by the investigator as not medically relevant.

- 3.1.9 The effects of IL-2 on the developing human fetus are unknown. For this reason and because chemotherapeutic agents are known to be teratogenic, women of child-bearing potential and men must agree to use adequate contraception (hormonal or barrier method of birth control; abstinence) prior to study entry and for the duration of study participation. Should a woman become pregnant or suspect she is pregnant while participating in this study, she should inform her treating physician immediately.
- 3.1.10 Ability to understand and the willingness to sign a written informed consent document.

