7.1.8 Administration

After reconstitution, an up to 2-week IL-2 supply will be provided in single-use syringes (in a cool-pack if necessary), for home refrigerator storage at 2-8 C. One single-use syringe will be used each day during home SC self-administration, and discarded in the sharps' containers provided. Participants will be instructed to rotate injection sites, if feasible.

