9. STUDY CALENDAR

Table 2: Summary of Required Data

	Within 4 Wks prior (baseline)	During Therapy (End of Wks 1, 2, 4, 6, 8, 9, 10, 12, 14) ^a	End of Wk 16 ^a	Extended-duration IL-2 (4 Wkly) ^c
Medical History	X	X	X	X
Physical Exam	X	X	X	X
Toxicity Assessment		X	X	X
cGVHD Symptom Score	X	X ^b	X	X [#]
EKG	X			
Pregnancy Test [¶]	X			
Pulmonary Function	o	o ^b	o	o [#]
Dermatologic Assessment	o	o ^b	o	o [#]
Oral Assessment	o	o ^b	o	o [#]
Flexion Assessment	o	o ^b	o	o [#]
Ocular Assessment	o	o ^b	o	o [#]
CBC with Diff	X	X*	X	X
Serum Chemistry	X	X*	X	X
Quantitative Immune Globulins	X	X ^d	X	X ^δ
Immunology ¹	X	X	X	X ^δ
Steroid Assessment ²	X	X ^b	X	X ^δ
CMV Viral Load	X	X	X	X
Thyroid Function	X		X	X ^δ
Drug Diary ⁺		X	X	X

X- Required Evaluation

o- Required for patients with clinical involvement of these organ systems (oral and ocular assessments are optional), Baseline pulmonary function tests can be scheduled up to 4 weeks prior to start of treatment to 1 week after for scheduling flexibility.

1 Immunology: plasma banking; storage of additional mononuclear cells.

2 Systemic steroids should not be tapered unless there is toxicity, e.g severe hyperglycemia (with permission of study PI).

a Testing at end of weeks 1, 2, 4, 6, 8, 9, 10, 12, 14 will be performed ± 4 days, to allow for scheduling and administrative flexibility around weekends, holidays etc.

b Week 8 for steroid dose and cGVHD assessments.

c Testing during extended-duration therapy will be performed ± 2 weeks, to allow for scheduling and administrative flexibility around patient travel, work, holidays etc.

d Week 4, 8, 12.

CONFIDENTIAL

This document is confidential. Do not disclose or use except as authorized.

Phase II ECP and IL-2 for chronic GVHD

Version 2.0; August 15, 2016

* Laboratory testing of CBC/manual diff, serum creatinine and LDH will also be performed 4±2 days after IL-2 initiation, to assess for anemia, thrombocytopenia, schistocytes and/or renal dysfunction associated with thrombotic microangiopathy.

δ Every 8 weeks (±4 weeks) at time of mandatory study-center follow-up.

Every 16 weeks (+/- 4 weeks) during year 1 at time of mandatory study-center follow-up.

¶ For women of child-bearing potential.

+ To be completed and returned to clinic at least every 2 weeks during study IL-2 treatment. To be completed at and returned to clinic at least every 8 weeks for extended-duration IL-2.

CONFIDENTIAL

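### Section 6.2 restarts IL-2 without requiring unsupported counts, and names no hold for suspected or milder TMA although a TMA check is scheduled

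*Combined protocol and SAP*

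**What the plan says.** **Restart after severe hematologic toxicity (6.2).** IL-2 is withheld when ANC is below 500 or platelets are below 10,000 (read here as either one), provided the decline is "not related to malignant disease relapse, infection or other etiologies". Then: "If counts improve (ANC>1000, Plts>20,000) within 2 weeks, IL-2 will be restarted at 50% dose and not re-escalated". The stop rule follows: "If peripheral counts do not improve within 2 weeks, or drop again (ANC<500, Plts<10,000) after restarting IL-2, it will be discontinued".

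**Entry counts (3.1.8).** ANC must exceed 1000 and platelets 50,000, "without growth factors or transfusions".

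**TMA (6.2).** TMA during IL-2 "requires discontinuation of IL-2 if it is associated with CNS dysfunction, renal dysfunction requiring hemodialysis/CVVH, or need for hospitalization". The bullet gives no hold, work-up or restart step for anything less.

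**TMA surveillance (section 9, calendar footnote).** CBC with manual differential, creatinine and LDH are drawn 4±2 days after IL-2 starts, "to assess for anemia, thrombocytopenia, schistocytes and/or renal dysfunction associated with thrombotic microangiopathy". No dosing action is tied to the result.

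**Context.** In the earlier phase I trial, TMA was the dose-limiting toxicity in two participants (2.2.1.4). Section 6.1.1 calls it possibly related to IL-2 and says one of the two needed long-term hemodialysis. Patients inject at home: "an up to 2-week IL-2 supply will be provided in single-use syringes" (7.1.8).

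**The concern.** The restart test and the non-recovery stop both read the same count. If that count may be supported, a patient whose marrow or platelets have not recovered can pass the first and escape the second. The authors wrote the unsupported-count condition at entry but did not repeat it at restart.

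The protocol singles out TMA for an early laboratory check, yet the only TMA rule applies once the event is already severe. An early positive result has no instruction attached. Two investigators could act differently on the same smear, and home dosing continues until someone tells the patient to stop. What is at stake is patient safety and consistent dosing, not the primary test.

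**Working it through.** The plan gives no figure on this point, so the check is mainly a comparison of rules, with simple arithmetic for scale.

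**1. Restart test.** Inputs are the 6.2 limits: hold below 10,000 platelets, restart above 20,000.
- From an illustrative 9,000, the rise needed is more than 20,000 − 9,000 = 11,000. From any starting value, a rise of more than 20,000 is enough.
- The documents give no transfusion increment. Assumed increments of 10,000, 20,000 and 30,000 from 9,000 give 19,000 (not met), 29,000 (met) and 39,000 (met).

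A supported platelet count can therefore satisfy the rule, depending on the increment. If a transfused rise fades, a second fall below 10,000 after restart stops IL-2. The exposure is then the doses given between restart and that fall.

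**2. Which 6.2 rule would hold IL-2 for milder TMA?** As an illustration, take schistocytes, platelets of 15,000 and creatinine below grade 3.
- TMA bullet: not triggered without CNS dysfunction, dialysis/CVVH or a need for hospitalization.
- Grade 3 and grade 4 bullets: limited to non-hematologic toxicity, and the creatinine is below grade 3.
- Bullet for toxicity below grade 3: discretionary and non-hematologic.
- Hematologic bullet: platelets are not below 10,000.

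No named hold applies. By contrast, 6.2 does name a hold for grade 3 or higher infection before week 6 of IL-2, an event it says is not IL-2 related.

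**3. Test schedule.** Take IL-2 start as day 0 at the end of week 8, with no early start. The course is 8 × 7 = 56 doses. Tests fall on day 4±2 and then nominally on days 7, 14, 28, 42 and 56.
- From the TMA check to the next test: 7 − 4 = 3 days nominally, and at most 11 − 2 = 9 days using the ±2 and ±4 day windows.
- After weeks 10, 12 and 14, the next scheduled test is nominally 14 days later.

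These are intervals between scheduled laboratory panels, not between patient contacts.

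**4. Statistical figures.** The operating characteristics in 14.1 and 14.5 reproduce and do not depend on these rules. P(≥17 of 25) is 0.054 at 50% and 0.851 at 75% (stated 0.05 and 0.85). P(≥3 of 10) is 0.070, 0.617 and 0.945 at 10%, 30% and 50% (stated 0.07, 0.62 and 0.95).

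**The case against.** The strongest reply is that other text already covers most of the ground, and much of that stands.
- **Mandatory removal.** Section 5.6 requires removal when a 5.4 criterion applies. These include grade 4 events (except asymptomatic correctable laboratory results), recurrent or non-resolving grade 3 events, persistent or recurrent severe hematologic toxicity, and unacceptable events. Related grade 3 non-hematologic toxicity, such as renal toxicity, is held under 6.2.
- **Contact.** ECP is given twice weekly throughout the IL-2 weeks. The visits do not mandate LDH, creatinine or a smear, but patients are seen.
- **Likelihood.** Section 6.1.1 reports no platelet fall above 40% and no platelet transfusions in earlier transplant patients on low-dose IL-2. From the entry limit of 50,000, a 40% fall leaves 30,000; reaching 10,000 takes an 80% fall. The same section does report thrombocytopenia in the two TMA cases.
- **Force of the rules.** Section 6 calls them recommendations. It also says they are not mandatory in extended-duration treatment, which implies more weight during the 16-week study.

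Some stronger readings are tempting but unsupported:
- A reader might infer that the protocol accepts transfused counts for restart. It is silent, and improvement may well have been meant as true recovery.
- A reader might infer that nothing can stop IL-2 in milder TMA. Sections 5.4 and 5.6 can, partly through judgment.
- A reader might infer that TMA falls outside the hematologic hold as another etiology. Section 6.1.1 calls the earlier cases possibly IL-2 related, so this is ambiguous. The listing of TMA as an expected transplant event in 11.4.1 concerns reporting, not dosing.
- A reader might carry 2/28 = 7.1% into this trial. That figure pools three dose levels, and both patients were on a calcineurin inhibitor with sirolimus, a pair now excluded (3.2.2). Prior TMA is also excluded (3.2.3).

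**Conclusion.** The point holds in a narrow form. As written, 6.2 can restart IL-2 on supported counts, and it names no hold for suspected or milder TMA even though a test for it is scheduled. What remains uncovered is the patient with early or milder TMA outside the removal criteria, and the patient whose recovery is supported. Either drug of the excluded pair is still allowed alone, and 6.1.1 names TMA as a complication of each, so excluding the pair reduces the concern without removing it.

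How often either situation would arise cannot be estimated from the documents. No sample size, error rate or power figure changes. The conclusion rests on reading 6.2 literally; the transfusion increments and the example patient are assumptions used for illustration. This is a cheap safety improvement of low priority.

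**What to change.** **Hematologic bullet.** Add to the restart condition: *without transfusion or growth-factor support, and with TMA not suspected*. The count limits, the two-week window, the directive to restart, the half dose and the bar on re-escalation all stay.

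**TMA bullet.** Add: *Withhold IL-2 for suspected TMA (e.g. schistocytes with new thrombocytopenia, rising LDH or rising creatinine), including on the 4±2 day check, pending work-up. If TMA is excluded, resume at the prior dose unless another 6.2 rule applies. If TMA is confirmed but below the discontinuation criteria, restart only after resolution, at 50%, with Overall PI agreement.* The existing discontinuation criteria are unchanged.

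**Cost.** No new scheduled test is needed, though a smear may sometimes be wanted outside the planned manual differentials. Missed doses are not made up (Appendix J). Assumed false-alarm holds of 3, 7 or 14 days cost 3/56 = 5.4%, 7/56 = 12.5% or 14/56 = 25% of doses if the prior dose is resumed.

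Half-dose restart should be kept for confirmed TMA because it costs far more. After a hold at dose 4, a 7-day gap delivers 4 + 45 × 0.5 = 26.5 of 56 dose-equivalents, a 53% loss. For 3 and 14 days the losses are 49% (28.5 delivered) and 59% (23 delivered). Resuming the prior dose after a false alarm also matches 6.2, which allows it after infection.

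A 14-day hold leaves 42 days of IL-2, above the 4 weeks of ECP+IL-2 required by section 10. Only holds totalling more than 28 days, or stopping before day 28, fall short. The evaluability rule in 14.1 (one week of ECP) is not affected.

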7. DRUG FORMULATION AND ADMINISTRATION

7.1 IL-2

7.1.1 Description

Native interleukin-2 (IL-2) is a secreted glycoprotein with a molecular weight of approximately 15 kilodalton (kD). The gene for IL-2 was isolated from the Jurkat leukemia cell line and expressed in *Escherichia Coli*. In contrast to native IL-2, recombinant IL-2 is non-glycosylated and differs at two amino acid positions. There are no discernable functional differences between native and recombinant forms of IL-2.

IL-2 pharmacokinetics has been evaluated in patients with cancer and with HIV. Following a short IV infusion, the pharmacokinetic profile of IL-2 was characterized by high plasma concentrations, rapid distribution into the extravascular space, and elimination from the body with a half-life of 1-2 hours. After SC administration, absorption of IL-2 was slow and the mean resident time was prolonged compared with IV administration. Maximum plasma concentration of IL-2 in HIV patients was achieved within 2-5 hours after SC dosing and the terminal phase half-life was estimated at 5 hours, suggesting prolonged absorption. Data on SC IL-2 administration suggest that approximately 35% is absorbed into the bloodstream, with greater bioavailability (>60%) reported in HIV-infected participants.

There are at least 3 mechanisms of clearance of IL-2: glomerular filtration, peritubular extraction, and an inducible receptor-mediated mechanism (in man). Peri-tubular extraction of small peptides and proteins from the post-glomerular capillaries into the renal tubules and subsequent intracellular catabolism is a renal mechanism of elimination that occurs independent of glomerular filtration. Receptor-mediated clearance is primarily a function of IL-2 engaging its specific cellular receptor on responsive cells. The majority of IL-2 receptors are on T cells, and NK cells, though other cell types such as B cells have functional IL-2 receptors.

No pharmacologic interactions with other agents are anticipated in-vivo.

